13.1 DSMB

The DSMB will review the safety, ethics and outcomes of the study. The DSMB is responsible for monitoring cognitive and safety outcomes for early dramatic benefits or potential harmful effects and provide reports to the SC on recommendations to continue or temporarily halt recruitment to the study. The DSMB will be governed by a charter that will outline their responsibilities, procedures and confidentiality. They will review unblinded data from the study at regular intervals during follow-up and monitor treatment adherence differences between the two groups, drop-out, and event rates. It is anticipated that the first data review will be conducted after the first 50 participants have achieved 6 months of follow-up, and 6-monthly reviews thereafter.

13.2 Definitions & Reporting

13.2.1 Adverse Events

An AE is defined as any untoward medical occurrence in a patient or clinical investigation participant administered a pharmaceutical product at any dose and which does not necessarily have a causal relationship with this treatment. Therefore, an AE can be any unfavourable and unintended sign (including an abnormal laboratory finding, for example), symptom, or disease temporally associated with the use of an investigational medicinal product (IMP), whether or not it is considered related to the IMP. This definition includes intercurrent illnesses or injuries, and an exacerbation of a pre-existing condition.

13.2.2 AESI

The expected adverse reactions to the study medication that will be used in this study that are of special interest are listed below. To better assess participants' tolerability to the study medications, the following AESIs and whether they are new or ongoing from baseline, will be reported in the eCRF at specified visits, regardless of severity and seriousness:

- myalgia
- nausea
- elevation in blood glucose
- elevation in creatinine kinase
- abdominal pain
- new-onset diabetes mellitus
- rhabdomyolysis

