6.4.2 Exclusion Criteria

1. Evidence of dementia and/or significant cognitive impairment on screening (i.e. Blind Montreal Cognitive Assessment [MoCA] score $< 19/22$)
2. Severe co-morbid medical or psychiatric condition that prevents participation
3. History of traumatic brain injury with loss of consciousness (> 30 mins) within the last 2 years
4. Ongoing long-term use, or clear indication (e.g. secondary cardiovascular prevention in high-risk individuals) or contraindication (e.g. previous adverse reaction) for statin use
5. Evidence of severe or significant liver disease, defined as any of the following: acute viral hepatitis; chronic active hepatitis; cirrhosis; or elevated biochemical function markers, i.e. alanine aminotransferase (ALT) or aspartate aminotransferase (AST) $> 3x$ the upper limit of normal (ULN) or estimated glomerular filtration rate (eGFR) $< 30\text{mL}/\text{min}/1.73\text{m}^2$
6. Creatine kinase (CK) levels $> 2x$ upper limit of normal (ULN)
7. Female of child-bearing potential that is, unable or unwilling to use reliable method of contraception, breastfeeding, or planning a pregnancy
8. *For a sub-group of participants undergoing MRI* – any contraindication to MRI due to metallic body parts or claustrophobia
9. Medical history that might, in the opinion of the attending clinician, put the participant at significant risk if they were to participate in the trial

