6.6 Schedule of Evaluations

Table 1: Schedule of Evaluations

Visit Number	0	1	2	3	4	5
Time (Weeks [w]/Months [m])	-1m to 0	0	6w	6m	12m	18m
Window Period	-	-	±1w	±1m	±1m	±1m
Visit Type	Online + Phone	Clinic*	Phone	Clinic*	Phone	Clinic*
Remote / Electronic Informed Consent	X					
In-person Written Informed Consent		X				
SPHERE Questionnaire	X	X				
Blind MoCA	X					
Eligibility – Inclusion/Exclusion Criteria	X	X				
Medical History, Demographics & Socio-Economic Status		X				
Pregnancy Test – where required		X				
Lifestyle – Smoking, Diet, Alcohol		X		X		X
History of Health Service Use for COVID-19/Visits to Medical Professionals		X		X		X
Anthropometrics – Height & Weight		X				X
Blood Pressure, Heart Rate		X		X		X
Fasting Bloods	Haematology/Electrolytes/Renal/Liver Function – full blood count, Na, K, urea, nitrogen, creatinine, eGFR, ALT, AST, CK		X			X
	Glucose/Lipids/Inflammation – glucose, total cholesterol, LDL, HDL, triglycerides, CRP		X			X
	Neurodegenerative Biomarkers – 220 participants		X			X
Cognitive Assessments – SDMT, RAVLT-D, OTMT-A, OTMT-B, D-KEF-CWIT, SF		X		X		X
Health Assessments – PHQ-9, GAD-7, PSQI, EQ-5D-5L		X		X		X
Actigraphy plus Sleep Diary – 7-day Capture		X		X		X
Brain MRI – 220 participants		X				X
Dispense Study Medication – treatment arm only		X		X	X	
Study Medication Adherence & Accountability – treatment arm only			X	X	X	X
Concomitant Medications		X	X	X	X	X
SAEs/AESIs			X	X	X	X

*For participants who cannot attend the clinic, efforts will be made for visit assessments to be conducted remotely via tele-/videoconference.

ALT – Alanine Aminotransferase

AST – Aspartate Aminotransferase

CK – Creatine Kinase

CRP – C-Reactive Protein

D-KEF-CWIT – Delis-Kaplan Executive Functioning System “Stroop” Colour-Word Interference Test

GAD-7 – Generalised Anxiety Disorder-7

HDL – High-Density Lipoprotein

LDL – Low-Density Lipoprotein

MoCA – Montreal Cognitive Assessment

MRI – Magnetic Resonance Imaging

PSQI – Pittsburgh Sleep Quality Index

RAVLT-D – Rey Auditory Verbal Learning Test – Delayed Recall

SDMT – Symbol Digit Modalities Test

SF – Semantic Fluency

SPHERE – Somatic and Psychological Health Report

eGFR – estimated Glomerular Filtration Rate
EQ-5D-5L – EuroQoL 5-Dimensional 5- Level Questionnaire

OTMT – Oral Trail Making Tests A & B
PHQ-9 – Patient Health Questionnaire-9

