6.7.2 Visit 1 – Screening, Baseline & Randomisation

After preliminary screening, potentially eligible participants who have provided remote consent will be invited to attend a morning appointment at a research clinic in a fasting state to complete the screening process and, if eligible, baseline assessments. (If required e.g. if results of blood tests are not available on the same day, the visit can be split across 2 days). If participants are unable to attend these clinics and are otherwise eligible and willing to participate in the study, efforts will be made to conduct all assessments remotely.

At the screening visit, the following assessments will take place:

- Informed consent
- Eligibility assessment
- Review of participant's demographics, socio-economic status and lifestyle – smoking, diet and alcohol intake
- Review of participant's medical history including health service use
- Measurement of height and weight
- BP and HR
- Blood sample – following an overnight fast
 - Haematology/electrolytes/renal/liver function – full blood count, sodium, potassium, urea, nitrogen, creatinine, eGFR, ALT, AST, CK
 - Glucose/lipids/inflammation – glucose, total cholesterol, low-density lipoprotein (LDL), high-density lipoprotein (HDL), triglycerides, CRP
 - *Neurodegenerative biomarkers (sub-study group: 220 participants)*
- Cognitive Assessments
 - Symbol Digit Modalities Test (SDMT), Rey Auditory Verbal Learning Test – Delayed Recall (RAVLT-D), Oral Trail Making Test (OTMT) (A & B), Delis-Kaplan Executive Functioning System “Stroop” Colour-Word Interference Test (D-KEF-CWIT), Semantic Fluency (SF)
 - Cognitive assessments will be undertaken in a separate session within 7-10 days of the clinical assessment by research personnel with skills in cognitive measures. Personnel conducting cognitive assessments will be kept blind to the participants' treatment allocation. Treatment allocation (randomisation) will be undertaken by the research coordinator using the study database following review of the participant's routine blood tests.
- Health Assessments
 - Patient health questionnaire 9 (PHQ-9), generalised anxiety disorder 7 (GAD-7), Pittsburgh sleep quality index (PSQI), EuroQoL 5-Dimensional 5-Level Questionnaire (EQ-5D-5L)
- Provision of actigraphy watch and sleep diary

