6.7.3 Visit 2 – 6 Weeks (\pm 1 Week) – Telephone

The following will be assessed at the 6-week phone call:

- Review of any SAE/AESIs since last visit
- Adherence to study medication (participant-reported) – treatment arm only
- Changes to concomitant medications

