7.2 Blinding

Study treatment is open-label. The randomisation allocation will be blinded to researchers conducting cognitive assessments and endpoint adjudicators. All participants, physicians and other study team members will be aware of participant treatment allocation. However, participants will only be informed of their allocation after all the baseline assessments have been completed in order to reduce the risk of differential withdrawal between the two arms.

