20.14 Appendix 14 – NPS SAMS

Statin-associated muscle symptoms (SAMS)

Use a systematic approach to assess suspected statin intolerance

[figure not shown]
- Statin intolerance is rarely life-threatening and may have a lower incidence than is commonly reported.^{2,4}
- Statins have been associated with a nocebo effect, whereby patients experience adverse effects based on the expectation of harm from a treatment.⁵
- For muscle-related adverse effects:
 - ▼ Incidence of statin-associated myalgia is lower in blinded RCTs (1% to 5%)³ compared to observational studies (7% to 29%).⁴
 - ▼ Myopathy incidence is ≈ 1 in 10,000 per year.⁴
 - ▼ Rhabdomyolysis incidence is ≈ 1 in 100,000 per year.⁴
- Involve patients in assessing and managing adverse effects.
- Advise patients to contact you if they experience muscle symptoms, and not to stop taking their statin.⁶

SAMS Assessment Guide

SAMS LESS LIKELY			SAMS MORE LIKELY	
Unilateral Non-specific distribution Tingling, twitching, shooting pain, nocturnal cramps or joint pain	Nature of symptoms^{4,6,7}		Bilateral Large muscle groups (eg, thighs, buttocks, calves, shoulder girdle) Muscle ache, weakness, soreness, stiffness, cramping, tenderness or general fatigue	
Onset before statin initiation Onset > 12 weeks after statin initiation			Timing of symptoms⁴	
Non-statin causes of muscle symptoms including: • conditions eg, hypothyroidism, polymyalgia rheumatica • vitamin D deficiency • unaccustomed/heavy physical activity • medicines eg, glucocorticoids, antipsychotics, immunosuppressant or antiviral agents	Other considerations^{4,7}		Risk factors for SAMS including: • medicine or food interactions • high-dose statin therapy • history of myopathy with other lipid-modifying medicines • regular vigorous physical activity • impaired hepatic or renal function • substance abuse (eg, alcohol, opioids, cocaine) • female • low BMI	
			CK levels⁴	
If SAMS is likely, proceed to the SAMS Management Algorithm (see overleaf)				

References available online at:
nps.org.au/statins-card-refs

SAMS Management Algorithm

CK = creatine kinase, LDL-C = low density lipoprotein cholesterol, ULN = upper limit of normal
 * CK > ULN and weakness demonstrated upon physical examination. † Higher potency statins with a long half-life are preferred for intermittent dosing eg, rosuvastatin and atorvastatin

Acknowledgements

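### AESIs must be classed as new or ongoing from baseline, but the schedule has no Visit 1 AESI record, leaving myalgia, nausea and abdominal pain without a proper pre-allocation comparator

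*Protocol*

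**What the plan says.** Section 13.2.2 lists seven AESIs: myalgia, nausea, raised blood glucose, raised creatine kinase (printed there as creatinine kinase), abdominal pain, new-onset diabetes and rhabdomyolysis. It says that "the following AESIs and whether they are new or ongoing from baseline, will be reported in the eCRF at specified visits", whatever their severity or seriousness.

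The specified visits are those in Table 1 (section 6.6). The row reads "SAEs/AESIs X X X X", and the four marks fall at Visits 2, 3, 4 and 5. Visits 0 and 1 are blank. The Visit 1 procedures in section 6.7.2 contain no AESI item. The first AESI task is in section 6.7.3, the 6-week telephone call: "Review of any SAE/AESIs since last visit".

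Section 7.2 describes who is unblinded by then: "All participants, physicians and other study team members will be aware of participant treatment allocation". Blinding is kept for cognitive assessors and endpoint adjudicators. Sections 6.7.2 and 7.2 also say that participants are told their arm only once all baseline assessments are done.

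Visit 1 does collect related data. The bloods include "full blood count, sodium, potassium, urea, nitrogen, creatinine, eGFR, ALT, AST, CK" and "Glucose/lipids/inflammation – glucose, total cholesterol, low-density lipoprotein (LDL), high-density lipoprotein (HDL), triglycerides, CRP". Medical history is reviewed, and the SPHERE questionnaire is completed at Visits 0 and 1.

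**The concern.** A rule that separates new from ongoing events needs a record of what was present at the start, and this schedule does not provide one under the AESI heading. The population makes that matter. Participants enter because of persisting symptoms, identified by any positive SPHERE response with no score threshold, or by anosmia. SPHERE itself asks about limb pain, weak muscles, muscle pain after activity and nausea, so entry symptoms and AESIs overlap.

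If symptom status at entry is first reconstructed at 6 weeks by people who know the arm, the split into new and ongoing events can reflect expectation. The protocol's own Appendix 14 notes a nocebo effect with statins. Its assessment guide for statin-associated muscle symptoms, which section 7.4 says will be followed, also uses onset relative to treatment: "Onset before statin initiation" counts against a statin cause. A reliable account of symptoms before treatment is therefore useful for more than one purpose. No analysis plan can recover a pre-allocation symptom record that was never made.

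**Working it through.** The protocol gives no figure to reproduce here. The check sets the AESI list beside what Visit 1 collects.

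| AESI (section 13.2.2) | Visit 1 information | Usable as baseline? |
|---|---|---|
| CK elevation | CK in Visit 1 bloods | Yes, measured |
| Glucose elevation | Fasting glucose | Yes, measured |
| New-onset diabetes | Medical history plus fasting glucose | Yes |
| Rhabdomyolysis | Baseline CK; CK above 2 times the upper limit is excluded (section 6.4.2) | In effect, yes |
| Nausea | SPHERE item 9 | Coarse proxy |
| Myalgia | SPHERE items 4, 10, 11, 12 and 17 | Coarse proxies; no general myalgia item |
| Abdominal pain | No specific item (28 and 29 cover bowel habit and bloating) | No |

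None of the seven has a scheduled AESI entry at Visit 1. Three have direct baseline data, one is in effect covered, two have a partial proxy and one has no specific item: 3 + 1 + 2 + 1 = 7.

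SPHERE is a weak substitute for the three symptoms, for four reasons:

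- Its lowest response merges never with some of the time and is coded 0 (section 6.8.1 and Appendix 1). An intermittent symptom therefore scores as absent, whereas an AESI is reportable at any severity.
- It is not repeated after Visit 1, so there is no like-for-like comparison later.
- Its stated purpose is to assess long COVID symptoms at screening.
- No section names it as the AESI baseline.

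The effect on the comparison can be written down, though not evaluated. For one symptom AESI, let p be the share of participants with the symptom at entry, expected to be equal across arms by randomisation. Let a_T and a_C be the shares with a truly new event on atorvastatin and control. Let q_T and q_C be the probabilities that a symptom present at entry is labelled new. Assume that a participant with the symptom at entry cannot also have it as a truly new event, and set aside the reverse error. Then:

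- Observed new events: a_T + p·q_T on atorvastatin and a_C + p·q_C on control.
- Observed difference: (a_T − a_C) + p·(q_T − q_C).

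If q_T = q_C, the difference is unchanged, but both arms carry added false events. A ratio is pulled towards 1 and the comparison is noisier. If q_T and q_C differ, the difference is biased by p·(q_T − q_C), which can lie anywhere between −p and +p. The protocol gives neither p nor either q. The reverse error, a new symptom labelled as ongoing, is also possible and is equally unquantified.

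**The case against.** The strongest reply is that this is a scheduling omission with limited reach. Much of it stands. A reader might infer from the blank cell that no AESI has any baseline, but four of the seven are directly or in effect covered. The Visit 1 bloods, history and SPHERE are also obtained before participants learn their arm, so what is missing for those four is only a stated link.

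A reader might also infer that entry symptoms will be counted as new mainly on atorvastatin. The protocol does not establish this. The AESI row is not restricted to the treatment arm, so controls are asked the same questions. AESIs are reported whether new or ongoing, so totals by arm do not depend on the label. Section 11.3 plans descriptive safety summaries. Bias needs misclassification that differs by arm, which open-label treatment makes plausible but not certain.

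A third tempting step is to size the problem from Appendix 14, which gives statin-associated myalgia as 1% to 5% in blinded trials and 7% to 29% in observational studies. With 410/2 = 205 per arm, that would be about 2 to 10 people against 14 to 59. Those ranges compare study designs. They say nothing about having or lacking a baseline checklist, and a checklist would not remove nocebo symptoms that truly begin after treatment starts.

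Finally, the stop and restart strategies in Table 2 turn on severity and judged cause, not on the new/ongoing field, so it goes too far to say that the gap drives those decisions.

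What survives is that, for myalgia, nausea and abdominal pain, section 13.2.2 asks for a classification that the schedule does not support.

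**Conclusion.** The inconsistency between section 13.2.2 and Table 1 with section 6.7.2 is real, and it is confined in practice to three symptom-only AESIs: abdominal pain most clearly, and myalgia and nausea through inadequate proxies. As written, their new/ongoing status would rest on recall after allocation is known. The consequence is possible bias in the comparison of new events if misclassification differs by arm, or a blurred comparison if it does not. Neither direction nor size can be fixed from the protocol, which gives no prevalence at entry and no misclassification rate.

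The conclusion assumes that the study forms follow the protocol as written and that no unstated instruction adds a Visit 1 symptom entry. The primary and key secondary outcomes are not affected. Myalgia is the most consequential of the three because the synopsis names it as a safety outcome. The change is worth making because it is cheap and cannot be made good once participants know their arm.

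**What to change.** - **Table 1 and section 6.7.2:** mark the SAEs/AESIs row at Visit 1. Add a short record of the presence and severity of myalgia, nausea and abdominal pain, completed in both arms before allocation is disclosed. The existing rule that participants learn their arm only after baseline assessments already makes room for this.
- **Section 13.2.2:** state that Visit 1 bloods and medical history are the baseline for CK, glucose and diabetes, with baseline CK also serving for rhabdomyolysis.
- **Visits 2 to 5:** classify each AESI as new or ongoing against that Visit 1 record, not by recall.

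The cost is a few minutes at a visit already held and a small protocol and eCRF amendment. The protocol does not show an existing AESI symptom form, so a brief one may have to be built. No change to the treatment-stopping or rechallenge rules is proposed.

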7.4 Management of Possible Treatment Related Side-Effects

The following strategies (Table 2) can be employed for participants with side-effects deemed due to study medication and sufficiently severe to warrant a change of treatment.

Table 2: Strategies for change in treatment due to side-effects

Clinical Scenario	Strategy
Clear contraindication to a statin	Ineligible
Mild symptoms of myalgia, nausea, dizziness	Temporarily stop study medication. If symptoms improve, restart study medication – subject to investigator’s discretion. If symptoms persist, study medication can be permanently stopped.
Moderate-severe symptoms of abdominal pain or myalgia, with/without biochemical or haematological abnormalities	Temporarily stop study medication. Factors to consider include renal impairment and other medications. On improvement, consider re-challenging with study medication and review. If symptoms persist, study medication can be permanently stopped. If severe reaction, permanently cease study medication and begin appropriate alternate treatment in accordance with local guidelines.

For possible or suspected Statin-Associated Muscle Symptoms (SAMS), the National Prescribing Service (NPS) process will be followed (see Appendix 14).

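### CK elevation as an AESI is open to ascertainment bias, because the only extra CK work-up stated in the protocol applies in practice to the atorvastatin arm alone

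*Protocol*

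**What the plan says.** Section 13.2.2 lists seven AESIs, one of them "elevation in creatinine kinase" (evidently creatine kinase, the term used in 6.4.2 and 6.6). They "will be reported in the eCRF at specified visits, regardless of severity and seriousness", with a note of whether each is new or ongoing from baseline. No CK threshold is given. Section 12.4 makes AESIs a safety outcome. Section 11.3 plans descriptive safety summaries, and the DSMB sees unblinded data (13.1).

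Scheduled CK is the same in both arms. It is named at Visit 1 (6.7.2) and at 18 months (6.7.6). The 6-month list (6.7.4) names fasting bloods including biochemistry and glucose, but not CK. At 6 weeks and 12 months there is a telephone call (6.7.3, 6.7.5) with "Review of any SAE/AESIs since last visit" and no blood sample.

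Unscheduled CK has one stated route. Section 7.4 concerns side-effects attributed to study medication and says: "For possible or suspected Statin-Associated Muscle Symptoms (SAMS), the National Prescribing Service (NPS) process will be followed". The assessment guide in Appendix 14 has a CK heading, and its algorithm footnote refers to CK above ULN. No corresponding work-up is stated for control participants with muscle symptoms. Section 7.2 states: "Study treatment is open-label". Only cognitive assessors and endpoint adjudicators are blinded.

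**The concern.** A laboratory AESI is found only if someone takes blood. If muscle symptoms lead to a CK test in one arm and not in the other, and any elevation from any source is counted, the tested arm will show more elevations even if the drug does nothing to CK.

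This population is likely to set off the trigger. The Introduction names fatigue and muscle weakness among the commonest long COVID symptoms, and Appendix 14 lists muscle ache, weakness and general fatigue as pointing towards a statin cause. Appendix 14 also describes a nocebo effect, and participants know what they are taking.

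The DSMB and readers will compare the CK rows by arm even though no formal test is planned. The first DSMB review comes when 50 participants have reached 6 months (13.1). If the 6-month panel omits CK, every CK value between baseline and 18 months is unscheduled, and unequal testing then has its greatest weight.

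**Working it through.** The protocol states no expected rate of CK elevation, so there is no figure to reproduce. The check has two parts.

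**1. Stated testing after baseline, by arm**

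| Test | Atorvastatin | Control |
|---|---|---|
| CK, scheduled | 1 (18 months), or 2 if 6-month biochemistry includes CK | the same |
| CK, triggered by the stated process | yes (7.4, Appendix 14) | none stated |
| Glucose, scheduled | 2 (6 and 18 months) | 2 |
| Glucose, triggered | none stated | none stated |

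The only asymmetry in the text is triggered CK.

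**2. Illustration with no drug effect on CK**

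Inputs:
- n = 410/2 = 205 per arm (11.1, equal groups).
- s = scheduled post-baseline CK tests, 1 or 2.
- q = share of the atorvastatin arm given one extra CK test. Appendix 14's myalgia figures serve as a stand-in: 1% to 5% (blinded trials) and 7% to 29% (observational studies).
- e = chance that any one CK test is raised. This is an assumption: 2%, 5% or 10%.
- Controls have no triggered tests, and tests within a person are independent (both assumptions).

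Control: P = 1 − (1 − e)^s. 
Atorvastatin: P = (1 − q)[1 − (1 − e)^s] + q[1 − (1 − e)^(s+1)]. 
The difference is q·e·(1 − e)^s, so extra cases = 205·q·e·(1 − e)^s.

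- Smallest (s = 2, q = 0.01, e = 0.02): 205 × 0.01 × 0.02 × 0.98² = 0.04 cases, or 0.02 percentage points.
- Middle (s = 2, e = 0.05): at q = 0.05, 9.75% v 9.98% (control v atorvastatin), 0.46 cases; at q = 0.29, 9.75% v 11.06%, 2.7 cases.
- Largest (s = 1, q = 0.29, e = 0.10): 205 × 0.29 × 0.10 × 0.90 = 5.35 cases, or 2.6 percentage points.
- Risk ratios over the grid run from 1.00 to 1.28.

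**Higher yield from triggered tests.** Suppose a triggered test is raised with probability e₂ = 10% to 30% (assumption), while scheduled tests stay at e = 5% with s = 2. Then extra cases = 205·q·e₂·0.95².

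- q = 0.05, e₂ = 0.10: 205 × 0.05 × 0.10 × 0.9025 = 0.93 cases, risk ratio 1.05.
- q = 0.29, e₂ = 0.30: 205 × 0.29 × 0.30 × 0.9025 = 16.1 cases, risk ratio 1.81.

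On the stated testing, the corresponding excess for glucose is 0.

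**The case against.** The strongest reply is that separating scheduled from unscheduled laboratory values is ordinary SAP and eCRF detail, that safety is only to be described, and that nothing bars a CK test in a control participant. The work-up's confinement to one arm is inferred from the scope of 7.4. The readable part of Appendix 14 does not say that every suspected case gets a CK test, and its algorithm figure was not available to me. These points stand as limits: the bias is a possibility, not an established fact. They do not remove the point, because the reporting rule that 13.2.2 does state produces the unequal count. A later SAP also cannot reliably separate the sources if the eCRF never captured them.

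Four stronger readings are tempting and are not supported.

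- **Glucose and new-onset diabetes share the problem.** "elevation in blood glucose" is an AESI too, but the readable muscle-symptom process contains no glucose test and scheduled glucose is equal. Extra testing by unblinded clinicians would be conjecture.
- **The telephone visits bias the comparison.** They are the same in both arms. They create reliance on outside tests, not a difference between arms.
- **Up to 18 extra cases.** One might multiply 0.29 × 205 = 59 triggered tests by a 30% yield. That does not subtract people already found by scheduled tests. With 30% for every test, the excess is 205 × 0.29 × 0.30 × 0.70 = 12.5 cases (s = 1) or 205 × 0.29 × 0.30 × 0.70² = 8.7 (s = 2). The 29% also comes from observational studies, not open-label randomised trials.
- **CK already raised at entry is miscounted.** Section 6.4.2 allows entry with CK up to 2× ULN, but the record of new or ongoing status partly covers this.

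A fair objection to the remedy is that participants with muscle symptoms may have stopped study medication (7.4) before the scheduled sample, so a scheduled-only comparison could miss on-drug elevations. That stands, and it is why the fix asks for both tables.

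**Conclusion.** The concern holds for CK alone. Detection of CK elevation is open to ascertainment bias: any severity counts, no cut-off is given, participants and physicians know the allocation, and the one stated route to extra CK testing operates in practice in the atorvastatin arm. The direction would be to overstate CK elevation on atorvastatin.

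The size cannot be fixed from the protocol. With no drug effect it runs from negligible (0.04 cases per 205) to about 5.4 at an assumed 2% to 10% yield per test, and to about 16 if triggered tests yield 30%. These figures rest on the assumed yields, on Appendix 14's myalgia rates as a proxy for triggering, on no triggered tests in controls, and on independent tests. Positive correlation between a person's tests would lower the excess at a given yield.

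The point is worth acting on because the remedy is cheap and works best before data are collected.

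**What to change.** - **eCRF:** add one field giving the source of each CK value, scheduled or symptom-triggered.
- **Sections 13.2.2 and 12.4:** base the between-arm comparison of CK elevation on samples scheduled in both arms, relative to the participant's Visit 1 value. Tabulate triggered elevations separately beside it, by arm. The working definition of elevation can be set in the SAP. Correct the enzyme's name in 13.2.2.
- **Sections 6.6, 6.7.4 and 6.7.6:** reconcile whether CK belongs to the 6-month panel. In the copy I read, the fasting-blood rows of Table 1 show two marks each, whereas the visit text has bloods at baseline, 6 and 18 months. The table may be damaged in extraction, so I rely on the visit text.

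The cost is protocol wording and one data field. The proposal itself requires no additional visit or sample, and patient management is unchanged. The downside is that the scheduled-only comparison can miss transient on-drug elevations in participants who had stopped study medication by the time of the sample. Both tables must therefore be reported, to the DSMB as well as in the final report.
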